## **5.2. Treatment Regimen**

Each ointment (8% RAPA and placebo) will be applied to the appropriately designated keloid (RAPA experimental or placebo control) once daily for 6 months.

To avoid treatment confusion, the chosen keloids will be marked with a color-code by permanent marker; one color will be red, and a second will be green. Metered dispensers will be similarly color coded. The dispenser coded in red will be applied to the keloid labeled "right" and the lime green coded dispenser will be applied to the keloid labeled "left." Participants will be given color-coded photographs of the 2

keloids with identified landmarks to show which keloid receives which color-coded ointment.

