### **5.3. Administration of Study Drug**

The initial application will be done in the laboratory for subject education. Color-coded permanent markers will be given to participants to re-mark sites as needed.

Participants will be responsible thereafter for applying the different ointments to the color designated keloids once daily for the study's duration. Two medication dispensers (8% RAPA and vehicle control) will be given to each subject on a monthly basis.

Subjects will be instructed to turn the Topi-CLICK of each container once per application and apply all the expressed ointment to the matching, color-coded keloid. Subjects will be instructed to apply ointments after bathing or showering, avoid washing the treated areas for at least 4 hours after application, avoid cross-contamination between sites by washing hands between applications, and use new disposable gloves (provided by study) for each ointment application.

By managing with color-coded dispensers to match lesions, the participants will be "blind" to which lesion is receiving placebo and which keloid gets active treatment.

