### **5.4. Subject Compliance Monitoring**

Subjects will be called weekly between Visits 1 and 2 to verify compliance and at midpoints between Visits 2 and 7. Subjects also receive a drug diary to help record administrations and any notable effects, which supports reporting the participant's experiences at phone follow-ups and clinic visits.

Each dispenser will be weighed before being given out and at monthly intervals to quantify compliance.

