#### **6.1.2. Screening and Baseline**

Following consent and signature, participants will undergo minimal cognitive screen ( $\text{CLOX1} \geq 10$  and  $\text{CLOX2} \geq 12$ ) to ensure consent is valid. Study staff will:

- Obtain vital signs, height and weight, lab work (fasting) to ensure safety and rule out systemic infection (complete blood count [CBC], comprehensive metabolic panel [CMP], lipid panel, and urine pregnancy test)
- Document medical history, concomitant medication review, physical examination, and
- Perform evaluation of eligibility criteria listed in Sections 4.1 – 4.2 above.

Additional baseline activities and data collection to include:

- Current and recent medications within past 3 months
- Marking of keloid lesions selected for study
- Photography and caliper measurements
  - Standard calipers will be used for measuring height of keloid above normal skin surface
  - Photography and use of Image J software – Study staff will upload digitized photographs and transfer directly from camera to computer software; images of the keloid are visualized, and outlined with an electronic drawing tool contained in the software. The software calculates the surface area within the outlined region and stores the data in Image J for analysis (see Analysis section next page).
- 1st medication administration for education
- Investigational medication prescribed/dispensed for 1 month, and participant is given written instructions for self-administering medication and care of the study lesion

- Schedule Visit 2

Study staff will contact participants weekly by phone for follow up (3 calls) during the first month of treatment. If the participant has a SmartPhone, a scheduled video visit (such as FaceTime, IMO or Skype) is optional to conduct weekly interim assessments but not required. Visits 2-7 must be performed in the research area and cannot be conducted virtually due to photography standardization.

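### As written, the two dispensers are told apart only by a red/lime-green code, with no colour-vision check and no check of which ointment reached which keloid

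*Combined protocol and SAP*

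**What the plan says.** Each participant treats one keloid with 8% rapamycin ointment and a second with petrolatum vehicle, once daily for 6 months. Section 5.2 (Treatment Regimen) sets out how the two are kept apart:

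- **Skin marks:** "the chosen keloids will be marked with a color-code by permanent marker; one color will be red, and a second will be green".
- **Dispensers:** "Metered dispensers will be similarly color coded". The red dispenser goes to the keloid labelled right, and "the lime green coded dispenser will be applied to the keloid labeled" left.
- **Photographs:** participants receive colour-coded pictures of the "keloids with identified landmarks to show which keloid receives which color-coded ointment".

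Section 5.3 adds that "The initial application will be done in the laboratory for subject education", that participants renew the skin marks themselves with the coloured markers, that they match dispenser to keloid by colour, and that two new dispensers are issued each month. Under section 6.1.2 the "participant is given written instructions for self-administering medication and care of the study lesion".

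Section 1.4 states that the ointments match in consistency and smell. Section 5.6 says the opaque container hides subtle differences between them.

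Section 5.4 (Subject Compliance Monitoring) provides calls, a drug diary and weighing: "Each dispenser will be weighed before being given out and at monthly intervals to quantify compliance".

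**The concern.** The purpose of the code is to prevent mix-ups, yet red and green are the pair that people with red-green colour deficiency may confuse. On the text, nothing else distinguishes one dispenser from the other: no word, letter, number, shape or side label on the container is described. A participant may know exactly which keloid is the right one and still not know which dispenser is the red one.

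The treatment comparison is made within each subject. Ointment on the wrong keloid therefore affects both halves of that subject's comparison: the active keloid loses doses and the control keloid gains them. With only 5 completers planned, one such subject carries a fifth of the mean contrast. The dispensing records and weights would still show full compliance.

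**Working it through.** The plan gives no figure on this point, and no effect size, SD or power calculation behind the 5 completers, so there is nothing to reproduce. The check has three parts.

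**1. Does any stated cue identify the dispenser without colour?**

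| Cue | Section | Identifies the keloid without colour? | Identifies the dispenser without colour? |
|---|---|---|---|
| Skin mark | 5.2, 5.3 | No | No |
| Right/left label | 5.2 | Yes | No; the side is tied to a dispenser colour |
| Landmark photograph | 5.2 | Yes | No; the link to the ointment is colour-coded |
| Dispenser code | 5.2 | Not applicable | No; red or lime green |
| Ointment and container | 1.4, 5.6 | Not applicable | No; alike by design |

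The supervised first application takes place once, with the first pair of dispensers; new pairs follow monthly. Colour vision is not mentioned in the eligibility criteria (4.1, 4.2), the Visit 1 procedures (6.1.2) or the visit schedule (6.8).

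**2. Would a planned check show a swap?** Each dispenser is turned once per application (5.3). It loses that amount wherever the ointment goes, so its monthly weight is the same with or without a swap. The calls and diary are described as recording compliance, administrations and notable effects, not the site each ointment reached. The image reviewers are blinded to treatment and subject (6.1, photography and caliper analysis), so they could not flag one.

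**3. Size.** Two separate quantities are involved.

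*Dilution.* Assume response is proportional to doses received, and that subjects have equal true effects. If a subject misplaces a fraction f of doses, the keloid meant for rapamycin receives 1-f of them and the control receives f. The contrast is multiplied by (1-f) - f = 1-2f. If one of 5 completers does this, the mean contrast is multiplied by (4 + 1-2f)/5 = 1-2f/5.

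| f | That subject: 1-2f | Five-subject mean: 1-2f/5 |
|---|---|---|
| 0.10 | 0.80 | 0.96 |
| 0.25 | 0.50 | 0.90 |
| 0.50 | 0.00 | 0.80 |
| 1.00 | -1.00 | 0.60 |

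If two of 5 did so, the mean multiplier would be 1-4f/5: 0.80 at f = 0.25 and 0.60 at f = 0.50.

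*Chance that at least one affected person is among the 5.* The formula is 1-(1-p)^m, where p is an assumed prevalence (the documents give none) and m is the number of people to whom it applies.

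| Assumption | Result |
|---|---|
| p = 0.5% of all participants, m = 5 | 2.5% |
| p = 2%, m = 5 | 9.6% |
| p = 4%, m = 5 | 18.5% |
| p = 8%, m = 5 | 34.1% |
| p = 5% of men, 3 men | 14.3% |
| p = 5% of men, 5 men | 22.6% |
| p = 10% of men, 3 men | 27.1% |
| p = 10% of men, 5 men | 41.0% |

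The range is therefore about 2.5% to 41%, and it depends heavily on the sex mix. Both sexes are eligible (4.1).

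**The case against.** The strongest reply is that the plan has several safeguards besides colour: right/left labels, landmark photographs, a supervised first application, written instructions, three calls in the first month with optional video, midpoint calls thereafter, a diary, and keloid observation at Visits 2 to 7. A participant who cannot tell the dispensers apart has occasions to say so, and a wrongly renewed skin mark could be seen at a visit. This stands against two inferences a reader might draw: that the colour code is the only safeguard, and that a swap must go unnoticed. It does not close the gap. The labels and landmarks identify the keloid rather than the dispenser, and none of the contacts is described as checking which ointment went where.

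The size could also be overread. The 2.5% to 41% concerns enrolling an affected person; the further step, the chance that such a person swaps given the other safeguards, is not in the documents. Nor is it right that 5 subjects provide no averaging. The repeated-measures model in 7.1 pools subjects, and one subject swapping 25% of doses leaves 90% of the mean contrast. Reversal of a subject's contrast needs f above 0.5, which is worse than choosing at random for each dose.

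Finally, the dispenser's green is specified as lime green, and some affected people may distinguish it from the red. The written instructions are not reproduced, and the drug-management SOP is listed as pending in section 15, so the containers may carry labels that the protocol does not describe. Both points stand as uncertainties and are why the finding is limited to what is written.

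**Conclusion.** The point holds as a minor operational gap. As written in 5.2 and 5.3, telling the dispensers apart rests on red versus lime green alone; no colour-vision check is planned, and no stated step confirms which ointment reached which keloid. A crossover is possible and would pull the rapamycin-versus-vehicle contrast toward zero for any f up to 0.5. For one affected subject in five, the plausible loss in the mean contrast is modest (10% at f = 0.25, 20% at f = 0.50), although that subject's own contrast would be halved or removed. These sizes rest on proportional response and equal effects. The documents do not support a claim that swaps are likely.

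**What to change.** In 5.2 and 5.3:

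1. Print RIGHT or LEFT on each dispenser and on each photograph, so that matching does not need colour.
2. Replace red and green with a pair not confused in red-green deficiency (for example blue and yellow) on dispensers, photographs and skin markers.
3. At each existing monthly visit, have the participant show which dispenser goes on which keloid. Record any mismatch and its likely start, so that it can be considered in the analysis.

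The printed side names only the site, which 5.2 already ties to a colour, so the blind is unaffected. The cost is new labels and pens, which the study already supplies in another colour, and about a minute per visit. No extra visit, staff or procedure is needed.

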### **5.3. Administration of Study Drug**

The initial application will be done in the laboratory for subject education. Color-coded permanent markers will be given to participants to re-mark sites as needed.

Participants will be responsible thereafter for applying the different ointments to the color designated keloids once daily for the study's duration. Two medication dispensers (8% RAPA and vehicle control) will be given to each subject on a monthly basis.

Subjects will be instructed to turn the Topi-CLICK of each container once per application and apply all the expressed ointment to the matching, color-coded keloid. Subjects will be instructed to apply ointments after bathing or showering, avoid washing the treated areas for at least 4 hours after application, avoid cross-contamination between sites by washing hands between applications, and use new disposable gloves (provided by study) for each ointment application.

By managing with color-coded dispensers to match lesions, the participants will be "blind" to which lesion is receiving placebo and which keloid gets active treatment.

### **5.4. Subject Compliance Monitoring**

Subjects will be called weekly between Visits 1 and 2 to verify compliance and at midpoints between Visits 2 and 7. Subjects also receive a drug diary to help record administrations and any notable effects, which supports reporting the participant's experiences at phone follow-ups and clinic visits.

Each dispenser will be weighed before being given out and at monthly intervals to quantify compliance.

### **5.5. Prior and Concomitant Therapy**

#### **5.5.1. Exclusionary medications:**

- Systemic steroid or immunosuppressant therapy
- Body lotions, astringents, or other skin applications including cosmetics and especially sunscreen to the keloid area(s)
- Other antifungal, antibiotic, or topical preparations

#### **5.5.2. Possible drug interactions:**

- See Section 5.1 above

### **5.6. Packaging**

Drug and placebo will be supplied by the compounding pharmacy in a metered dispenser called the Topi-CLICK® container. The opaque Topi-CLICK® dispenses 0.5-1mL of ointment, protects the product from light exposure, and serves to conceal any subtle differences between placebo and investigational product.

### **5.7. Management of Study Drug**

#### **5.7.1. Storage**

The compounded preparation of 8% RAPA in petrolatum will be stored in a locked cabinet at room

temperature in a cool, dry place.

### **5.7.2. Dispensing of Study Drug**

Designated study staff maintain the drug purchase documentation and administration logs to track how, when and to whom the investigational drug was assigned. Inventory is managed by the research pharmacy. Study clinical staff keep administration records regarding dosing compliance, returned/unused drug, and any damaged or wasted study drug product. Routine Study Drug reconciliation will be performed based on clinical site policy and standard operating procedures.

### **5.7.3. Return or Destruction of Study Drug**

The procedures for final reconciliation of the site's drug supply at the end of the study will be in accordance with research pharmacy standard operating procedures.

Unused study product will be disposed in accordance within the standard medication destruction policies of the hospital.

## **6. Study Procedures**

**Study visits.** All study visits will be performed at the Audie L. Murphy VA Hospital or by telephone.

### **6.1. Visit 1 – Consent, Screening and Baseline**

#### **6.1.1. Informed Consent**

Eligible subjects will be asked to come to the research area to review and sign the consent form. Staff conducting the consent process adhere to local standard operating procedure (SOP) for consent administration. When scheduling consent appointments, staff will ask participants to arrive fasting.

#### **6.1.2. Screening and Baseline**

Following consent and signature, participants will undergo minimal cognitive screen ( $\text{CLOX1} \geq 10$  and  $\text{CLOX2} \geq 12$ ) to ensure consent is valid. Study staff will:

- Obtain vital signs, height and weight, lab work (fasting) to ensure safety and rule out systemic infection (complete blood count [CBC], comprehensive metabolic panel [CMP], lipid panel, and urine pregnancy test)
- Document medical history, concomitant medication review, physical examination, and
- Perform evaluation of eligibility criteria listed in Sections 4.1 – 4.2 above.

Additional baseline activities and data collection to include:

- Current and recent medications within past 3 months
- Marking of keloid lesions selected for study
- Photography and caliper measurements
  - Standard calipers will be used for measuring height of keloid above normal skin surface
  - Photography and use of Image J software – Study staff will upload digitized photographs and transfer directly from camera to computer software; images of the keloid are visualized, and outlined with an electronic drawing tool contained in the software. The software calculates the surface area within the outlined region and stores the data in Image J for analysis (see Analysis section next page).
- 1st medication administration for education
- Investigational medication prescribed/dispensed for 1 month, and participant is given written instructions for self-administering medication and care of the study lesion

- Schedule Visit 2

Study staff will contact participants weekly by phone for follow up (3 calls) during the first month of treatment. If the participant has a SmartPhone, a scheduled video visit (such as FaceTime, IMO or Skype) is optional to conduct weekly interim assessments but not required. Visits 2-7 must be performed in the research area and cannot be conducted virtually due to photography standardization.

#### *Standardized digital photography and caliper measurements - Analysis*

We will measure keloid surface area and height changes pre-treatment and thereafter on a monthly basis using standardized digital photography with a tripod-mounted 8MP Canon S5is camera and calipers to measure keloid height (37). The key to successful use of photography is to maintain consistent image quality and thus ensure that images can be compared fairly. Factors that influence image quality will be standardized including lighting, 10cm distance from keloid surface, super macro camera setting, a proper center of focus perpendicular to the keloid surface, and inclusion of a standard millimeter ruler as a reference for calculation of surface areas by Image J. Photos thus taken will be suitable for sequential measurements over the 6 months of the study because they will be taken by the same camera at the same angle under identical conditions and using the same standardized ruler by the same person. Image J (<http://rsbweb.nih.gov/ij/index.html>), is a public domain image-processing program that can calculate area and pixel value statistics of user-defined selections, measure distances and angles, create density histograms, and line profile plots from digital images. Spatial calibration is available to provide real dimensional measurements in standard units such as mm^2. We used Image J to analyze our preliminary data and will use the same approach in this study. Surface areas of all photographed lesions will be measured with Image J by three trained reviewers blinded to all aspects of the photograph (date taken, treatment, subject, etc.). In addition, keloid height measurements (the maximum vertical elevation above normal skin) in millimeters will be made with calipers (37). Prior to measurements, we conduct training sessions for the readers to improve agreement among readers. Reviewers will be trained to standardized definitions (color, texture, etc.) of lesions thus minimizing inter-reviewer variability. We also will assess agreement within readers by repeating the measurements at a later time. The percentage of keloid flattening will be calculated as the percentage reduction normalized to pre-treatment height. Finally, we will record clinical observations of keloid changes to extend and subjectively verify our objective measurements.

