### 3.3. Study Endpoints

#### Primary outcome:

- Change in keloid surface area and keloid height

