## **9.3. Case Report Forms**

The study case report forms (CRF) are the primary data collection instruments for the study. Data requested on the CRF will be collected from the subject encounter and from the subject diaries, pharmacy logs, and medical records (VA CPRS), then entered into the REDCap database. All missing data will be routinely queried, corrected, and or explained. If a space on the CRF is left blank because the procedure was not done or the question was not asked, write "N/D". If the item is not applicable to the individual case, write "N/A".

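### Height is a primary measure alongside surface area, but the plan does not state that the caliper reader is blind, who holds the colour-to-drug code, or that allocation is random

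*Combined protocol and SAP*

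**What the plan says.** **Outcome.** Section 3.3 defines the primary outcome as "Change in keloid surface area and keloid height", in one line with neither measure ranked first. Section 2 puts both in the primary hypothesis. Section 7.1 applies repeated-measures ANOVA to both, at the 0.05 threshold.

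**Height.** The photography and caliper section (6.1.3 in the table of contents, unnumbered in the body) says that "keloid height measurements (the maximum vertical elevation above normal skin) in millimeters will be made with calipers". Section 6.1.2 says of baseline: "Standard calipers will be used for measuring height of keloid above normal skin surface". Sections 6.2 to 6.7 repeat the measurement at each visit.

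**Area.** The same photography and caliper section assigns area to "three trained reviewers blinded to all aspects of the photograph (date taken, treatment, subject, etc".

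**Participants and product.** Section 5.3 describes participants as blind "to which lesion is receiving placebo and which keloid gets active treatment". Section 1.4 says the two ointments match in texture and odour. Section 5.6 says the opaque dispenser hides small differences between them.

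**Colour code and records.** Section 5.2 marks one keloid red and the other green, colours the dispensers to match, and ties red to the keloid labelled right and green to the one labelled left. Section 5.7.2 says "Designated study staff maintain the drug purchase documentation and administration logs to track how, when and to whom the investigational drug was assigned" and also "Inventory is managed by the research pharmacy". Section 15 lists a drug-management SOP as pending.

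**The concern.** Finding the highest point of a lesion with calipers is a judgement made in person. If the person making it knows or believes which keloid is on rapamycin, the readings can drift towards the expected answer: lower on the active side, higher on the vehicle side, or both. The quantity of interest is the difference between the two keloids of one person, so the drift goes straight into the treatment contrast. It is directional, so repeating the measurement every month does not average it out.

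Surface area is guarded against this by blinded tracing, and a stored photograph can be traced again if the blinding is ever questioned. A past caliper reading cannot be taken again. The blinded area result checks area and says nothing about how height was read. If the plan stays silent, a report of this trial could claim blinded assessment for only one of its two primary measures.

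**Working it through.** The plan gives no figure to reproduce on this point. The check sets the two primary measures side by side, follows the colour code, and counts what is affected.

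**Step 1. The two measures compared**

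| Question | Surface area | Height |
|---|---|---|
| Where it is read | On a photograph, outlined in Image J | On the lesion, with calipers |
| Who reads it | Three trained reviewers | Not stated |
| Is the reader blind? | Stated, including to treatment | Not stated |
| Can it be re-read blind later? | Yes, from the stored image | No |

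Sections 3.2, 6.1.2 and 6.2 to 6.7 also mention the caliper measurement or carry it forward from visit to visit. None adds a reader or a statement of blinding.

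**Step 2. What a height reader's blindness depends on**

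A reader at the lesion can see a red or green mark. The colour alone does not reveal the treatment. The reader stays blind as long as he or she does not know which colour holds rapamycin. Three questions follow.

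- Which colour holds rapamycin, and is that chosen at random? Section 5.2 fixes colour to side but says neither. In the body of the plan, randomisation is mentioned only in Section 1.5, for a cited study.
- Is the choice made separately for each participant? Not stated. If one choice served everyone, learning it once would disclose the active side in all five; with separate choices it would disclose one.
- Who holds the key? Not stated. Section 5.7.2 comes nearest, with staff-kept logs and pharmacy-managed inventory, but it names no holder of the code.

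The table of contents lists no section on blinding, randomisation or code-breaking where the answers might otherwise be found.

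**Step 3. How much is affected**

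Inputs: 5 completers (Study Summary, Section 3.1), 2 keloids each (Section 3.2), and 7 measurement visits (baseline in Section 6.1.2, then Visits 2 to 7 in Sections 6.2 to 6.7).

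- Height readings: 5 × 2 × 7 = 70, of which 5 × 2 × 6 = 60 are after baseline.
- Within-person height contrasts: 5 × 7 = 35, of which 5 × 6 = 30 are after baseline.
- First-pass area tracings stated to be blind: 70 photographs × 3 reviewers = 210.
- Height readings stated to be blind: 0 of 70.

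These are planned counts for five complete participants. Sections 4.4.1 and 4.4.2 keep data from withdrawn participants and allow replacements, so the actual counts may differ.

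**Step 4. Size of any bias**

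It cannot be given. The documents report no caliper error and no baseline heights. The plan also expresses flattening as a percentage of pre-treatment height, so a shift in millimetres would have a different effect in each lesion.

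**The case against.** The strongest reply is that silence is not unblinding and that the plan already masks the product. That is right, and it rules out several stronger readings.

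- *A reader might infer that nothing protects the height comparison.* Matched ointments (Section 1.4) and an opaque dispenser (Section 5.6) do protect it in part, and neither safeguard is limited to participants. What they do not cover is a reader who knows the code.
- *A reader might infer that the caliper reader is unblinded.* No section says so. The code may be properly held in practice, and the pending SOP may record it.
- *A reader might infer that the logs give the treatment away.* Section 5.7.2 has staff record how, when and to whom drug was assigned, and Section 9.3 says "Data requested on the CRF will be collected from the subject encounter and from the subject diaries, pharmacy logs, and medical records". But every participant receives both dispensers (Section 5.3), so knowing who received drug does not show which lesion receives rapamycin. Neither section says that these records show what each colour contains.

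It can also be said that the photography and caliper section trains its readers and repeats measurements later. Whether that includes the caliper reader is unclear. In either case those steps improve agreement; they do not blind anyone.

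Finally, this is a five-completer pilot that also has safety and feasibility aims. That argues for a short, cheap remedy. It does not remove the point, because height is named as primary, is tested for significance, and is meant to inform a future trial.

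**Conclusion.** The point stands as a gap in the plan. Height has the same standing as surface area, yet assessor blinding is stated only for area. The plan does not say that the caliper reader is kept from the code, who holds the code, or that the colour or keloid receiving rapamycin is randomised. A team could follow the plan to the letter and still have height read by someone who knows the active side. The rapamycin-minus-vehicle height contrast is therefore open to directional assessor bias of unknown size, across all 70 planned readings.

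The conclusion rests on the text available. A few pages were removed from the copy reviewed, in the front matter, Section 1.3 and Section 8.3; none falls in Sections 3 to 7, where such a statement would be expected. If the pending SOP settles custody of the code, what remains is the unstated blinding of the height reader and the unstated randomisation. Confidence is medium, because actual practice may be better than the text. This should be fixed.

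**What to change.** Three short additions would close the gap.

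1. **Section 5.2.** The research pharmacy randomises, separately for each participant, which colour holds rapamycin. The rule tying red to right and green to left can stay, because only the contents of the two colours vary.
2. **Section 5.7.2 and the pending drug-management SOP.** The research pharmacy, which already manages inventory, holds the colour-to-drug code until the readings are locked. Clinic records show colour or kit number only. The conditions for breaking the code earlier are for the sponsor to set.
3. **The caliper paragraph.** Height is read by an existing staff member with no access to the code.

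Where any of this is already the practice, stating it is enough. The visit order and the existing log-keeping duties need not change.

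The cost is participant-specific labelling and restricted access to the code. With two dispensers a month for six months, five completers need 2 × 6 × 5 = 60 labelled dispensers. The outcome, the schedule and the analysis are unchanged. One risk remains: a visible local reaction on one lesion could still prompt a guess, so the change reduces the exposure without removing it.
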